3.2 Schedule of assessments (SoA)

Table 1. Schedule of assessments for long-term follow-up in COVID-19 patients.

| | COVID-19 (2 weeks ¹ ± 2 weeks) | 3 months ¹ (± 1 month) | 6 months ¹ (± 1 month) | 12 months ¹ (± 2 months) | 18 months ¹ (± 3 months) |
|--|---|--------------------------------------|--------------------------------------|--|--|
| Screening/baseline | | | | | |
| Inclusion criteria ¹ | X | | | | |
| Demographics ² | X | | | | |
| Healthcare setting ³ | X | | | | |
| Length of hospital stay, days | X | | | | |
| ICU admission | X | | | | |
| Medical history ⁴ | X | | | | |
| Treatment | | | | | |
| Comorbidity management ⁵ | X | X | X | X | X |
| Anti-COVID therapy ⁶ | X | | | | |
| Antibiotic therapy | X | X | X | X | X |
| Oxygen therapy ⁷ | X | X* | X* | X* | X* |
| SARS-CoV ² ⁸ and other respiratory pathogen vaccination ⁹ | X | X | X | X | X |
| Clinical assessment | | | | | |
| Relevant medical new events ¹⁰ | X | X | X | X | X |
| COVID-19 symptom ¹¹ onset | X | | | | |
| COVID-19 symptom end | X | X* | X* | X* | X* |
| COVID severity ¹² | X | | | | |
| SOFA score | X | | | | |
| Vital signs ¹³ | X | X | X | X | X |
| Physical examination ¹⁴ | X | X | X | X | X |
| 12-lead electrocardiography | X | X | X | X | X |
| 6-minute walking test | X | X | X | X | X |
| DLCO (diffusing capacity for carbon monoxide) | X | X | X | X | X |
| Pulmonary function test ¹⁵ | X | X | X | X | X |
| Questionnaires | | | | | |
| Functional status ¹⁶ | X | X | X | X | X |
| Respiratory impairment ¹⁷ | X | X | X | X | X |
| Mental health ¹⁸ | X | X | X | X | X |
| Risk perception and behaviour^{19, 20} | | | | | |
| SARS-CoV-2 vaccination: acceptance/non-acceptance and reasons ²¹ | | X | | X | X |
| Socio-economic indicators | | X | | X | X |
| Use of resources (COVID-19 unrelated) | | X | | X | X |
| Imaging | | | | | |
| Lung ultrasound | X | X | X* | X | X* |
| X-ray | X | X | X* | X* | X* |
| High-resolution CT scan | X | X | X* | X* | X* |
| Cardiac ultrasound | X | X | X* | X | X* |
| Cardiac MRI ²² | X ²¹ | X ²¹ | X* | X ²¹ | X* |
| Biochemistry | | | | | |

| | | | | | |
|---|---|-------------------|-------------------|-------------------|----|
| Blood tests ²³ | X | X | X* | X | X* |
| Arterial blood gas test (pO ₂ /pCO ₂ /pH) | X | X | X* | X* | X* |
| Urine tests ²⁴ | X | X | X* | X | X* |
| Immunology | | | | | |
| Immune - serology and type I IFNs autoantibodies | X | X | X | X | X |

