| Immune - cytokine and chemokine | X | X ³⁵ | X ³⁵ | X ³⁵ | X* |
| Immune - cellular | X | X ³⁵ | X ³⁵ | X ³⁵ | X* |
| Microbiological tests-NP swabs | | | | | |
| Viral variant and metagenomics sequencing | X | X*, ³⁴ | X*, ³⁴ | X*, ³⁴ | X* |
| EDTA whole blood | | | | | |
| Genetic and epigenetic analysis | X | X | X | X | X |
| Stool Sample (faeces or rectal swab) | | | | | |
| Metagenomic sequencing | X | | X | | X |
| Microbiological tests | | | | | |
| SARS-CoV-2 molecular test in nasopharyngeal swab or tracheal aspirate or bronchoalveolar lavage or saliva | X | X* | X* | X* | X* |
| Adjunctive variables for specific fragile populations | | | | | |
| HIV | | | | | |
| HIV-infection status ²⁵ | X | X | X | X | X |
| HIV-Infection therapy ²⁶ | X | X | X | X | X |
| Assessment of adherence to follow-up visits and antiretroviral therapy | X | X | X | X | X |
| Elderly | | | | | |
| Cognitive status ²⁷ | X | X | X | X | X |
| Pregnant women/new born | | | | | |
| History of positive SARS-CoV-2 molecular test on amniotic fluid or breast milk ²⁸ | X | | | | |
| History of detection of microthrombotic disease on placenta tissue or umbelical cord tissue | X | | | | |
| Children | | | | | |
| History of positive SARS-CoV-2 molecular test on amniotic fluid or breast milk ²⁹ | X | | | | |
| Biometric paramethers ³⁰ | X | X | X | X | X |
| Transplant | | | | | |
| Transplant general information ³¹ | X | | | | |
| Graft function ³² | X | X | X | X | X |
| Immunosuppressive regimen ³³ | X | X | X | X | X |

| Onco-haematology | | | | | |
|---|---|---|---|---|---|
| Assessment of adherence to oncologic follow-up visits and therapy | X | X | X | X | X |
| Assessment of progression of the disease and relapse | X | X | X | X | X |
| Assessment of adverse events ³⁴ | X | X | X | X | X |

Footnotes

Modular data capture according to level of commitment (level I, level II, level III).

| | |
|-----------------|--|
| Level I | Assessments in level I are mandatory |
| Level II | Customized according to the feasibility of each cohort |

* Reassessed only if outside the normal ranges at the previous assessment or if clinically indicated

1. Day 0: first positive SARS-CoV-2 test

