12. STUDY VARIABLES

Endpoint variables:

- Infection with SARS-CoV2 detected by RT-PCR on respiratory/saliva specimens;
- Reinfection and/or clinical relapse defined according to recent proposed definitions (7);
- Clinical spectrum of COVID-19 according to WHO mild, moderate, severe, and critical criteria (<https://www.who.int/publications/i/item/WHO-2019-nCoV-clinical-2021-1>);
- Duration of viable viral shedding in fragile patients diagnosed with COVID-19;
- Immune response in patients diagnosed with and/or vaccinated against COVID-19 assessed according to study protocol procedures (see above);
- All-cause mortality during the follow-up period;
- Change in basal clinical condition assessed by questionnaire on functional status and/or according to specific parameters of underlying fragile condition (i.e. graft function, cancer stage etc).

Baseline variables will include:

- Demographic data (sex, date of birth, ethnicity, blood group);
- Underlying conditions;
- Vaccination status against respiratory infectious diseases (i.e. Influenza, pneumococcus, BCG) if available.

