13. STATISTICAL ANALYSIS

We will carry out comprehensive descriptive analyses taking into account sociodemographic factors and clinical courses. The frequency distributions of the characteristics will be given in absolute and relative numbers, median plus interquartile range (IQR) or mean values plus 95% confidence interval (CIs). Associations with specific epidemiological features, laboratory results, therapeutic and preventive (including vaccination) strategies will be analysed using chi-square tests, t-tests or Mann-Whitney tests, depending on the data. To evaluate potential risk factors, multivariate regression models will be carried out. Outcome time analyses using Cox proportional-hazards regression models with time-dependent covariates will be performed to examine factors associated with each endpoint (including death). In addition, we will use cumulative incidence functions, such as the Fine-Gray sub-distribution hazard regression model, to account for competing events (i.e., death in evaluating graft function etc.). For missing values, a different strategy to understand the causes and the significance for the analysis will be developed and a graduated procedure for dealing with censorship and imputations via linked regressions will be developed. The significance level is defined with a p-value <0.05. Risk perception and socio-economic factors will be analysed using quasi-

experimental techniques (eg: propensity score matching, difference-in-differences) by exploiting several sources of variation over time and across individuals. All statistical analyses will be carried out with STATA, Python and/or R statistics software by trained staff (epidemiologists, statisticians) using the latest analysis methods.

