2.1 CHARACTERISATION OF SARS-COV-2 VIRAL VARIANTS (TASK 6.2)

This task will target two main points among selected patient populations: [i] to characterise the viral variants and to identify variants of concern (VOCs) by whole genome sequencing (WGS) in COVID-19 patients and in vaccinated individuals with breakthrough infections, and [ii] to study potential

mutation selection in populations presenting with long viral replication or receiving immunoglobulin therapies, and [iii] to study the viral replication (viral load and excretion duration).

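### Scheduled molecular tests place viral clearance only within a 33–122 day interval for patients still positive at the first visit, yet shedding duration is an endpoint under a blanket Cox plan, with no provision for interval censoring or a viability assay

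*Protocol*

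**What the plan says.** Section 12 of the protocol includes "Duration of viable viral shedding in fragile patients diagnosed with COVID-19" among seven unranked endpoint variables. It gives no rule for deriving the duration. Annex 4, section 2.1 (Task 6.2) shares the aim: "to study the viral replication (viral load and excretion duration".

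Table 1 in section 3.2 sets the follow-up schedule for patients with COVID-19, counted from "Day 0: first positive SARS-CoV-2 test". The relevant row is "SARS-CoV-2 molecular test in nasopharyngeal swab or tracheal aspirate or bronchoalveolar lavage or saliva". It carries a plain mark at the first visit (2 weeks ± 2 weeks) and an asterisked mark at months 3, 6, 12 and 18. The asterisk means "Reassessed only if outside the normal ranges at the previous assessment or if clinically indicated".

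Section 13 states: "Outcome time analyses using Cox proportional-hazards regression models with time-dependent covariates will be performed to examine factors associated with each endpoint". It adds that a procedure for censoring and imputation will be developed, without naming interval censoring.

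**The concern.** A Cox model in its usual form needs an event time that is observed, or known to exceed a censoring time. Clearance of virus is never observed directly. It is known only to lie between the last positive and the first negative test. That matters little when tests are close together, but here the two scheduled tests that bracket most clearances are one to four months apart. A patient positive on day 14 who clears on day 20 and one who clears on day 55 leave the same scheduled record: positive on day 14, negative at about day 90.

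Two things are at stake. First, prolonged shedding, which is of obvious interest in immunocompromised patients, could be overstated. Second, many centres contribute cohorts, and each may time visits differently within the permitted windows. A difference between fragile populations could then come from visit dates rather than from clearance.

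There is also a mismatch of measurement. The endpoint is viable shedding, but the documents list molecular tests and sequencing and no assay of viability.

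**Working it through.** The protocol gives no figure for this endpoint (no sample size, event count or expected duration), so there is none to reproduce.

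**Step 1: the gap, from the windows alone.** Inputs are from Table 1: first visit on day 0–28, second at 3±1 months. With 1 month = 30.44 days, the second window is day 61–122.

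- Minimum gap: 2 × 30.44 − 28 = 33 days
- Nominal gap: 3 × 30.44 − 14 = 77 days
- Maximum gap: 4 × 30.44 − 0 = 122 days

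This needs no assumption about how long patients shed. It applies to patients still positive at the first visit. A patient already negative there has clearance placed between day 0 and that visit, and need not be retested at month 3.

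**Step 2: recorded duration if the first-negative visit is the event date.** The documents give no shedding duration, so these inputs are assumptions: lognormal duration with log-SD 0.6; visit 1 uniform on day 0–28, visit 2 on day 60–120, visit 3 on day 150–210; no unscheduled tests; recorded duration = date of the first visit at or after true clearance; 400,000 simulated patients per setting.

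| True median (days) | Recorded median (days) |
|---|---|
| 10 | 25 |
| 15 | 68 |
| 20 | 78 |
| 30 | 87 |

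At a true median of 20 days, 70% are recorded at 60 days or more, against a true share of about 3%. The median width of the interval containing the true clearance time is 67 days.

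**Step 3: first-visit timing alone, true median 20 days.** Both cohorts comply with Table 1.

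| First test | Recorded median (days) | Recorded ≥60 days |
|---|---|---|
| Day 0–7 | 90 | 99% |
| Day 21–28 | 27 | 37% |

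**Step 4: effect of interim tests, true median 20 days.** Add one routine test, uniform on day 28–45 (also an assumption).

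| Share of patients with the interim test | Recorded median (days) | Recorded ≥60 days |
|---|---|---|
| None | 78 | 70% |
| Half | 41 | about 43% |
| All | 35 | 17% |

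With the interim test in everyone, the contrast in step 3 falls to 39 versus 27 days, with 17% at 60 days or more in both cohorts.

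**Step 5: what Cox regression on visit dates would return.** Different assumption: Weibull durations with shape 1.5 and a true hazard ratio for clearance of 0.6 between two groups; visits uniform in the Table 1 windows; one sample of 2,000 per row.

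| Reference-group median (days) | HR, true times | HR, visit dates | Correlation, recorded with true duration |
|---|---|---|---|
| 8 | 0.59 | 0.82 | 0.50 |
| 14 | 0.57 | 0.86 | 0.56 |
| 21 | 0.58 | 0.76 | 0.58 |
| 30 | 0.66 | 0.76 | 0.73 |
| 45 | 0.60 | 0.68 | 0.83 |

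For reference medians up to 21 days, recorded duration explains at most 0.58² = 0.34 of the variance in true duration. At 45 days it explains 0.83² = 0.69.

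**Step 6: no true difference, but different visit habits.** Two groups have the same Weibull distribution (400 patients in total). One is seen in months 2–3 and the other in months 3–4, both inside the 3±1 month window. Cox regression on visit dates gave mean hazard ratios of 0.32, 0.29 and 0.45 for true medians of 14, 21 and 30 days, with p<0.05 in 60 of 60 runs each.

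**The case against.** **Choice of method belongs to the analysis plan.** A reader might infer that the Cox model will analyse visit dates as clearance dates. The protocol does not say so. It gives no event date for this endpoint and defers censoring to a later procedure, and an analysis plan not shown may specify interval-censored methods. That stands, so the misdating is conditional. But section 13 does name Cox for every endpoint, which for this one is the wrong stated method. No analysis plan can supply scheduled tests between day 28 and about day 61.

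**Other dated tests exist.** A reader might also infer that visit dates are the only dates available. That is not supported. Day 0 is itself a test date, the asterisk footnote permits clinically indicated tests, section 11 takes swabs or saliva at visits for the underlying condition, and section 14.5 draws clinical data from the medical file. Step 4 shows how much such tests can help. None of these sources is a serial schedule for shedding, and the protocol does not say they will be used to derive the duration.

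**The size depends on unknowns.** A claim that recorded duration mostly reflects visit timing, whatever the truth, goes too far. The documents give no true duration, and the link to truth is much stronger for long shedding (step 5). Nor do they say that cohorts differ systematically in when they make the first visit. The contrasts in steps 3 and 6 show what the windows permit, not what will happen.

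**Limits of what can be read.** Figure 1 is not visible and the add-on substudies appear by title only, so denser sampling there cannot be excluded. Annex 4 schedules swabs at day 0 and then month 3, but they serve sequencing and the clinical protocol takes precedence, so nothing here rests on that table.

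**Weight.** Shedding duration is one of seven endpoints and is in neither list of objectives. That limits the importance of the point but does not remove it.

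**Conclusion.** The point holds in a bounded form. The firm part is arithmetic on Table 1: for a patient positive at the first visit and negative at the next, scheduled data place clearance only within 33 to 122 days (77 nominally). The protocol pairs that with Cox regression and provides for neither interval censoring nor a viability assay.

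The conditional part is the size of the distortion. It requires that the first-negative visit date be used as the event date and that few interim tests exist. Under the assumptions of step 2, a true median of 20 days is then recorded as about 78 days, and two compliant cohorts with identical shedding can be recorded at 90 and 27 days. With one interim test per patient the 78 falls to about 35, and with long true shedding the recorded value tracks the truth more closely. The documents do not establish that the distortion will occur. They leave it possible where a change of wording could prevent it.

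**What to change.** In sections 12 and 13:

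1. Define the endpoint as the interval from the last positive to the first negative dated molecular test. Use every dated test in the medical file, including clinically indicated and routine ones, as well as the scheduled visits.
2. Analyse it with an interval-censored survival model (parametric or otherwise) in place of Cox.
3. Name it duration of molecular (RNA) positivity, unless a viability assay is specified.
4. For cohorts with no tests between day 28 and month 2, do not report a duration. Report the proportion positive at the first visit, adjusted for day of test, and the proportion positive at month 3. Count explicitly the patients not retested because the repeat test was conditional.

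The cost is revised analysis wording and the entry of routine test dates. Duration estimates will be wider and less precise, reflecting what the schedule can show. An interval-censored model removes the misdating but does not shorten the gap, so precision will depend on how many interim tests are found.

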13. STATISTICAL ANALYSIS

We will carry out comprehensive descriptive analyses taking into account sociodemographic factors and clinical courses. The frequency distributions of the characteristics will be given in absolute and relative numbers, median plus interquartile range (IQR) or mean values plus 95% confidence interval (CIs). Associations with specific epidemiological features, laboratory results, therapeutic and preventive (including vaccination) strategies will be analysed using chi-square tests, t-tests or Mann-Whitney tests, depending on the data. To evaluate potential risk factors, multivariate regression models will be carried out. Outcome time analyses using Cox proportional-hazards regression models with time-dependent covariates will be performed to examine factors associated with each endpoint (including death). In addition, we will use cumulative incidence functions, such as the Fine-Gray sub-distribution hazard regression model, to account for competing events (i.e., death in evaluating graft function etc.). For missing values, a different strategy to understand the causes and the significance for the analysis will be developed and a graduated procedure for dealing with censorship and imputations via linked regressions will be developed. The significance level is defined with a p-value <0.05. Risk perception and socio-economic factors will be analysed using quasi-

experimental techniques (eg: propensity score matching, difference-in-differences) by exploiting several sources of variation over time and across individuals. All statistical analyses will be carried out with STATA, Python and/or R statistics software by trained staff (epidemiologists, statisticians) using the latest analysis methods.

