9. PATIENT COHORTS

The ORCHESTRA fragile population consists of 29 cohorts of 10 different fragile populations including pregnant women/new-born, children, patients with HIV infection, patients with autoimmune disease, solid organ transplant recipients, patients with oncological and hematological diseases, patients with cystic fibrosis, patients with Parkinson Disease and rheumatological diseases from from 14 countries (5 European and 9 non-European countries), with approximately 19784 subjects. Among these, 10.300 individuals are already registered in local databases and on active follow-up in the respective centers. A description of the cohorts is presented in the following sections.

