For patients with a past and/or new diagnosis of SARS-CoV2 infection/COVID-19 disease a pre-established long-term follow-up including multiple diagnostic levels in order to adapt to all the participating cohorts is requested. A detailed overview of the schedule of the study visits and the clinical parameters to be recorded is shown in **Table 1**. Patients who have already had COVID, and new patients being diagnosed with COVID, who can be followed up to at least 12 months, and for whom data can be collected according to **Table 1** should be included. In specific fragile cohorts, such as children cohorts, virtual assessments are allowed.

For patients who have been or will be vaccinated against COVID-19 during the study period, a pre-established monitoring of safety and efficacy in terms of immunological response will be performed. A detailed overview of the schedule of the clinical and laboratory parameters to be recorded is shown in **Table 2**. Patients who have already been vaccinated, or will be vaccinated, who can be followed for 12 months, and for whom data can be collected according to Table 2 should be included. The monitoring should start from the days of first and second dose administration when possible (i.e. vaccination administered in the same center where the patient is followed for the fragile condition), alternatively patients will be monitored at 3±1, 6±2 and 12±3 months after the first vaccination dose.

- Vaccination safety will be assessed by a dedicated questionnaire (Annex 3) distributed to patients at baseline or during the first monitoring visit.

- Vaccination efficacy will be established analyzing the immune response at the predefined time-points. The humoral immune response to vaccination will be assessed by a serological assay able to detect anti-Spike and anti-Nucleocapsid antibodies as well as seroneutralization assays in sera samples. The latter will be useful to exclude possible natural infection at the baseline (1st/2nd dose, or first post-vaccination monitoring visit). The cytokine and cell-mediated immune response to vaccination will be assessed in a subgroup of patients by centralizing samples to a referral laboratory, according to local ethic rules and budget. The number of SARS-CoV-2 paucisymptomatic or symptomatic infection despite vaccination will be also assessed by SARS-CoV-2 detection in respiratory/saliva sample.

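### Section 13 names only independent-sample tests for associations and no handling of cohort or repeated visits, so pooled contrasts that differ between cohorts could be confounded and anti-conservative

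*Protocol*

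**What the plan says.** Section 13 assigns associations with epidemiological features, laboratory results and therapeutic or preventive strategies to a short list of tests: they "will be analysed using chi-square tests, t-tests or Mann-Whitney tests, depending on the data". For risk factors it adds: "To evaluate potential risk factors, multivariate regression models will be carried out". Time-to-event endpoints get Cox models with time-dependent covariates, with Fine-Gray models for competing events. Propensity matching and difference-in-differences are named for risk perception and socio-economic factors only. On error it says: "The significance level is defined with a p-value <0.05".

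The section mentions no stratification by cohort, centre or country, no random effect, no robust variance, no paired test and no repeated-measures model.

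Section 9 describes "29 cohorts of 10 different fragile populations", from 14 countries, "with approximately 19784 subjects". Tables 1 and 2 in section 3.2 each have five assessment columns. For vaccinated patients, section 11 starts monitoring on the dose days when possible; "alternatively patients will be monitored at 3±1, 6±2 and 12±3 months after the first vaccination dose". Section 6 wants information on the fragile cohort as a whole and on each subgroup. Section 7 speaks of each cohort.

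**The concern.** Chi-square, two-sample t and Mann-Whitney tests need independent observations, and the latitude section 13 allows is only a choice among tests of that kind. The design departs from independence in two ways.

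**Cohort.** Recruitment differs sharply. Pedianet is primary care (9.8.1). EPICO is children attended in hospital with confirmed infection (9.8.3). Bahia is pregnant women admitted with suspected COVID-19 (9.8.4). THSTI enrols women within 20 weeks of gestation (9.11). Serology may be run on different platforms (Annex 4, Appendix 1, section 2.2). A pooled comparison of infection, severity or antibody level across a factor whose frequency differs by cohort mixes that factor with these differences. Vaccination and treatment strategies plausibly differ in this way. Understated variance is one consequence. Confounding is the other, and a variance correction alone does not remove it.

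**Patient.** Immune response and change in clinical condition are endpoints in section 12 and are measured repeatedly, but no method for correlated measurements is named for them.

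At stake are false-positive associations between populations, vaccines or treatments, and lost power where change within patients is tested as if the visits came from different people.

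**Working it through.** The protocol states no sample-size, power, ICC or design-effect figure, so there is nothing of its own to reproduce.

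**Inputs from the protocol.** About 19,784 subjects and 29 cohorts (section 9); significance level 0.05 (section 13; two-sided is my assumption); up to five visits (Tables 1 and 2).

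**Assumptions.** Equal cohort sizes, outcome ICC 0.001 to 0.05, and within-patient correlation ρ of 0.3 to 0.7. Mean cohort size m = 19784/29 = 682.2.

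Throughout, the true type I error of a nominal two-sided 5% test is 2 × [1 − Φ(1.96/√DE)], where DE is the ratio of true to assumed variance.

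**1. Factor constant within cohort, pooled test.** DE = 1 + (m − 1) × ICC = 1 + 681.2 × ICC.

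| ICC | DE | Effective N = 19784/DE | True type I error |
|---|---|---|---|
| 0.001 | 1.68 | 11,768 | 0.13 |
| 0.005 | 4.41 | 4,490 | 0.35 |
| 0.01 | 7.81 | 2,532 | 0.48 |
| 0.05 | 35.06 | 564 | 0.74 |

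**2. Factor varying partly between cohorts.** DE = 1 + (m − 1) × ICC of exposure × ICC of outcome. With exposure ICC 0.1:
- outcome ICC 0.01: DE = 1 + 681.2 × 0.001 = 1.68, error 0.13
- outcome ICC 0.05: DE = 1 + 681.2 × 0.005 = 4.41, error 0.35

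**3. Factor balanced within every cohort.** DE is about 1 − ICC: 0.99 at ICC 0.01 (error 0.049) and 0.95 at ICC 0.05 (error 0.044).

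**Simulation check.** Pooled chi-square test, 29 cohorts of 682, outcome prevalence 0.20, 2,000 runs:

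| Factor | ICC 0.01 | ICC 0.05 |
|---|---|---|
| Constant within cohort | 0.48 | 0.74 |
| Partly between cohorts (exposure ICC 0.1) | 0.12 | 0.34 |
| Balanced within cohorts | 0.047 | 0.052 |

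The formulas and the simulation agree closely.

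**4. Repeated visits.** If five visits entered as separate rows, a between-patient contrast would have DE = 1 + 4ρ. An unpaired test of change within patients would have DE = 1 − ρ.

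| ρ | Between-patient DE | Error | Within-patient DE | Error |
|---|---|---|---|---|
| 0.3 | 2.2 | 0.19 | 0.7 | 0.019 |
| 0.5 | 3.0 | 0.26 | 0.5 | 0.006 |
| 0.7 | 3.8 | 0.31 | 0.3 | 0.0003 |

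The direction of the error therefore depends on the contrast.

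**The case against.** A reader might infer that all 19,784 patients and all their visits go into single tests as independent rows, so that p-values and intervals throughout are far too optimistic. The protocol does not say so. The 19,784 is a head count, section 7 frames the objectives by cohort, and nothing states that visits are stacked. Steps 3 and 4 also show that the error is not general: contrasts balanced within cohorts are close to nominal, and unpaired tests of change are conservative. Many factors in the quoted sentence are patient-level and can vary within a cohort.

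A reader might also infer that fragile condition and cohort cannot be separated. That is true only of some populations. Parkinson disease is listed only for LIH (9.10) and cystic fibrosis only for UNIVR (9.4). But six partners recruit HIV-positive subjects (9.1, 9.3, 9.4, 9.6, 9.7, 9.9), and five recruit solid organ transplant recipients (9.1 to 9.5). Measurement is partly centralised too: section 11 sends T-cell and cytokine samples to one laboratory and stool to another.

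Finally, strata, random effects and variance estimators are often left to a statistical analysis plan, which is not at hand, and section 13 excludes no adjustment.

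These points limit the size and scope of the concern but do not remove it. Section 13 commits the association analyses to named tests, which is more than leaving detail open. Section 6 wants results for the fragile cohort as a whole, so pooled analyses are foreseeable. Error in the conservative direction is still error.

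**Conclusion.** The point holds in a limited form. As worded, section 13 supplies suitable tests for a single cohort at a single visit, and nothing explicit for pooled or repeated data. If the named methods were applied to pooled data, contrasts that differ between cohorts would be confounded by cohort and anti-conservative. The inflation runs from almost none to severe, depending on how far the factor varies between cohorts and on an ICC that the protocol does not give. The figures above illustrate that range and do not estimate the study's actual error rate. They assume pooling, equal cohort sizes and a two-sided test. The confounding argument needs none of these three assumptions beyond pooling: it needs only that both factor and outcome differ by cohort, which the recruitment rules make likely. The change is worth making before analysis, and it calls for no new data.

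**What to change.** Amend section 13 as follows:

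- Keep chi-square, t and Mann-Whitney tests for description within one cohort at one visit.
- For pooled analyses of factors that vary within cohorts, use models stratified by cohort or with a cohort effect, and say that this includes the Cox and Fine-Gray models.
- For repeated immune and questionnaire outcomes, use mixed models or GEE that allow for correlation within patient.
- Where a population comes from a single cohort, such as Parkinson disease, report its contrast with other populations as a descriptive cohort-level comparison. Stratifying by cohort would remove that contrast altogether, and no model can separate the condition from the cohort.

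The cost is a few sentences in section 13, slightly more analysis work, and wider intervals for between-cohort contrasts. Visits, samples and recruitment are unaffected.
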